4.2.2. Outcome Definitions and Measures

The registry is designed to observe several aspects of MDR-TB treatment such as drug utilization characteristics, treatment outcomes (clinical and microbiologic), and safety outcomes (adverse events and mortality). All study outcomes will be documented by the healthcare provider and will be reported up to 24 months after discontinuation of MDR-TB treatment.

Study outcome definitions will include:

- Medical indication for BDQ treatment as reported by the healthcare provider
- Frequency of use of expert medical consultation in MDR-TB treatment with BDQ
- Drug susceptibility of MDR-TB isolates (Pre-XDR, XDR) and drug susceptibility to BDQ based on MIC reported

-
- Laboratory location and type performing susceptibility testing as well as type of test performed
 - Past treatment history, past medical history, prior medications utilization, and health care site of treatment
 - Use of DOT for drug administration
 - Adverse events including deaths over the course of MDR-TB therapy recorded using WHO guidance for pharmacovigilance of medicines used in the treatment of tuberculosis (WHO 2012²⁵)
 - Comorbidities prior to initiating MDR-TB therapy as well as over the course of therapy
 - Concomitant medications prior to initiating MDR-TB therapy as well as over the course of therapy
 - Reason for discontinuation of MDR-TB therapy
 - Change in TB background regimen (Y/N)
 - Cavities on chest x-ray
 - Acid fast bacilli-smear $\geq 1+$ (Y/N)

The following definitions will be used for treatment outcomes among MDR-TB cases (WHO, 2013³⁰):

- Cured: Treatment completed as recommended by the national policy without evidence of failure AND three or more consecutive cultures taken at least 30 days apart are negative after the intensive phase^a.
- Treatment Completed: Treatment completed as recommended by the national policy without evidence of failure BUT no record that three or more consecutive cultures taken at least 30 days apart are negative after the intensive phase^a.
- Treatment Failed: Treatment terminated or need for permanent regimen change of at least two anti-TB drugs because of:
 - Lack of conversion^b by the end of the intensive phase^a, *or*
 - Bacteriological reversion^b in the continuation phase after conversion^b to negative, *or*

-
- Evidence of additional acquired resistance to fluoroquinolones or second-line injectable drugs, *or*
 - Adverse drug reactions (ADRs).
- Died: A patient who dies for any reason during the course of treatment.
 - Lost to Follow-Up: A patient whose treatment was interrupted for 2 consecutive months or more.
 - Not Evaluated: A patient for whom no treatment outcome is assigned. (This includes cases “transferred out” to another treatment unit and whose treatment outcome is unknown)
 - Treatment Success: The sum of cured and treatment completed

^a For *Treatment failed*, lack of conversion by the end of the intensive phase implies that the patient does not convert within the maximum duration of intensive phase applied by the program. If no maximum duration is defined, an 8-month cut-off is proposed. For regimens without a clear distinction between intensive and continuation phases, a cut-off 8 months after the start of treatment is suggested to determine when the criteria for *Cured*, *Treatment completed* and *Treatment failed* start to apply.

^b The terms “conversion” and “reversion” of culture as used here are defined as follows:

Conversion (to negative): culture is considered to have converted to negative when two consecutive cultures, taken at least 30 days apart, are found to be negative. In such a case, the specimen collection date of the first negative culture is used as the date of conversion.

Reversion (to positive): culture is considered to have reverted to positive when, after an initial conversion, two consecutive cultures, taken at least 30 days apart, are found to be positive. For the purpose of defining *Treatment failed*, reversion is considered only when it occurs in the continuation phase.

The following definitions will be used for treatment outcomes among non MDR cases or MDR status not documented (WHO 2013³⁰):

- Cured: A pulmonary TB patient with bacteriologically confirmed TB at the beginning of treatment who was smear- or culture-negative in the last month of treatment and on at least one previous occasion.
- Treatment Completed: A TB patient who completed treatment without evidence of failure BUT with no record to show that sputum smear or culture results in the last month of treatment and on at least one previous occasion were negative, either because tests were not done or because results are unavailable.

-
- Treatment Failed: A TB patient whose sputum smear or culture is positive at month 5 or later during treatment.
 - Died: A TB patient who dies for any reason before starting or during the course of treatment.
 - Lost to Follow-Up: A TB patient who did not start treatment or whose treatment was interrupted for 2 consecutive months or more.
 - Not evaluated: A TB patient for whom no treatment outcome is assigned. This includes cases “transferred out” to another treatment unit as well as cases for which the treatment outcome is unknown to the reporting unit.
 - Treatment success: the sum of cured and treatment completed.

Appropriate use of BDQ encompasses aspects of drug utilization such as whether or not treatment was initiated in an eligible patient at the earliest opportunity, the patients’ treatment history, medical history, concomitant medication use, type of facility dispensing treatment, whether lab confirmation is documented, indication for use (i.e., drug resistant versus drug sensitive versus latent infection versus extra-pulmonary versus non-tuberculosis mycobacteria infections), documentation of treatment outcome (clinical and microbiologic). Safety data will include the collection of adverse events, serious and non-serious, concomitant medications, and concurrent diseases/diagnoses which may impact the reported event or its resolution; data on deaths will be collected along with attribution. Treatment adherence will be measured by the percent of prescribed doses taken as directly observed therapy. Adherent will be defined as taking greater than 80% of prescribed doses. Non-adherent will be defined as taking 80% or fewer of the prescribed doses.

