1.3. STUDY OBJECTIVES

1.3.1. Primary Objectives:

The following primary objectives were specifically chosen to address gaps in the currently available data informing BDQ benefits and risks:

- To describe the type of hospital or outpatient setting administering MDR-TB treatment
- To describe MDR-TB treatment delivery modalities, including treatment and management programs in place, administration of drug under closely monitored conditions, and consultation with experts in clinical management of MDR-TB and public health authorities such as national MDR-TB advisory groups within National TB Control Programs
- To describe the demographic and clinical characteristics of MDR-TB patients participating in the registry
- To describe MDR-TB treatment regimen utilization including dosages, duration, past treatment history, past medical history, concomitant medications used for conditions other than TB
- To measure adherence to WHO guidance in terms of selection of MDR-TB regimens and selection of patients for BDQ treatment

- To describe the indication for use of BDQ
- To measure extent to which patient informed consent is obtained for receipt of BDQ
- To describe BDQ and background drug susceptibility testing expressed as minimum inhibitory concentration (MIC) at baseline and for isolates from the last positive specimens
- To actively monitor adverse events using cohort event monitoring, including the monitoring for drug-drug interactions
- To actively monitor for mortality events using cohort event monitoring that includes collection of cause of death where available
- To estimate the relative risk of adverse events and mortality events by comparing event rates among BDQ-treated patients to respective event rates among patients not treated with BDQ, adjusting for potential imbalances in predictors of receiving BDQ for treatment, as well as predictors of mortality, assuming the availability of comparable populations
- To describe the following treatment outcomes separately for patients with MDR-TB and patients with non- MDR cases or MDR status not documented, as stipulated by the WHO revised definitions for resistant TB cases in 2013: cured, treatment completed, treatment failed, died, lost to follow-up, not evaluated, and treatment success
- To compare the treatment outcomes of cured, treatment completed, treatment failed, died, lost to follow-up, not evaluated, and treatment success between BDQ-treated patients and patients not treated with BDQ

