2. OVERVIEW OF STUDY DESIGN

2.1. Study Design

The research design uses a prospective observational comparative cohort study of patients treated for MDR-TB in multiple countries included in the early adopter (WHO pilot) program. A case of tuberculosis is one in which a health worker (clinician or other medical practitioner) has diagnosed TB. MDR-TB is defined as TB caused by *Mycobacterium tuberculosis* resistant in vitro to the effects of isoniazid and rifampicin, with or without resistance to any other drugs. Patients are enrolled in the registry by their healthcare provider once the healthcare provider diagnoses a patient with MDR-TB (inception cohort for comparison) or decides to treat with BDQ (exposure cohort specifically identifying indication for use for BDQ). All patient follow-up data will be collected at each visit from the healthcare provider during the course of BDQ treatment and for an additional 24 months after the last BDQ dose unless the patient is lost to follow-up or has died. Similar follow-up will be conducted for MDR-TB patients not treated with BDQ. Two options are under evaluation for the recruitment of MDR-TB patients not treated with BDQ. The first option under consideration is to include patients who are eligible for BDQ, but refuse BDQ at sites where BDQ is available. The second

option under consideration is the use of a stepwise cluster wedge design to enroll patients at centers who would be eligible for BDQ, but do not have access. The method for selecting MDR-TB patients not treated with BDQ will depend on how BDQ is made available in the early adopter countries. All patients newly diagnosed and treated for MDR-TB will be eligible for inclusion in the registry. Additionally, all patients initiating BDQ treatment will be eligible for inclusion in the registry regardless of the indication for use. All patients meeting the inclusion criteria and providing informed consent for participation in the study will be enrolled. The registry enrollment period will be open for 36 months with an additional 24 months of follow-up for safety assessment. This enrollment period should allow the enrollment of approximately 3000 MDR-TB patients treated with BDQ.

Data will be collected in an observational manner such that the management of the patient is determined by the patient and the caregiver and not influenced by the registry protocol. The registry will describe care as it is provided.

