4.4.2. Analysis of Study Objectives

4.4.2.1. Descriptive Analyses

This analysis will describe and summarize the prescribing and utilization of MDR-TB treatments, as well as patient treatment outcomes (clinical and microbiologic), and TB isolate susceptibility. MDR-TB treatment will be summarized by patient demographics and clinical characteristics (comorbidities and concomitant medications). In addition, the details of MDR-TB treatment will be described including indication of use, dose, frequency, duration of use, usage with TB background regimen, and susceptibility of concomitant TB treatment regimens. Patients treated with BDQ outside of the MDR-TB indication will be summarized by patient demographics and clinical characteristics including indications of use, frequency, duration of use, usage with TB background regimen, and susceptibility of concomitant TB treatment regimens. Additionally,

treatment outcomes will be described separately for MDR-TB cases and non MDR cases or MDR status not documented (WHO, 2013³⁰).

Proportions and 95% confidence intervals will be estimated separately for BDQ-treated patients and non-BDQ-treated patients for each study objective.

Additionally the following treatment outcomes will be estimated separately for patients with MDR-TB for BDQ-treated patients and non-BDQ-treated patients: cured, treatment completed, treatment failed, died, lost to follow-up, not evaluated, and treatment success.

Analyses of MDR-TB drug susceptibility will use the total number of MDR-TB patients included in the registry. Proportions will describe the number of subjects whose post-enrollment isolates exhibit at least 4-fold increase in BDQ MIC in comparison to baseline MIC, provided that the post-baseline MIC is >0.25 mg/mL based on phenotypic methods on solid or liquid media. Additional proportions will describe the number of patients with pre-XDR and XDR-TB.

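### Comparing *cured* and *treatment completed* separately between groups mixes drug effect with how often cultures were taken and recorded

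*Protocol*

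**What the plan says.** Protocol 4.2.2 defines *cured* for MDR-TB cases as treatment finished under national policy "without evidence of failure AND three or more consecutive cultures taken at least 30 days apart are negative after the intensive phase". *Treatment completed* has the same opening condition, followed by "BUT no record that three or more consecutive cultures taken at least 30 days apart are negative after the intensive phase". The parallel definition for non-MDR cases says openly that such a record may be lacking "either because tests were not done or because results are unavailable". Treatment success is the sum of the two categories.

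No culture schedule is set. Section 2.1 states: "Data will be collected in an observational manner such that the management of the patient is determined by the patient and the caregiver". Section 3.1.3.1 has data recorded at enrolment and at each later visit.

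A primary objective in 1.3.1 is "To compare the treatment outcomes of cured, treatment completed, treatment failed, died, lost to follow-up, not evaluated, and treatment success between BDQ-treated patients" and those not given BDQ. Section 4.4.2.1 plans estimates by group for "cured, treatment completed, treatment failed, died, lost to follow-up, not evaluated, and treatment success", as proportions with 95% confidence intervals. It names no lead category.

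Section 2.1 leaves open where the non-BDQ patients come from: patients who decline BDQ at sites that offer it, or a stepped-wedge arrangement with centres that lack access.

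**The concern.** Two patients with the same bacteriological course can fall into different categories because one clinic cultured often enough to put three qualifying negatives on record and the other did not. If such practice differs between the groups, *cured* and *treatment completed* move in opposite directions with no difference in drug effect. A higher *cured* proportion under BDQ could then be read as effectiveness when part or all of it is laboratory follow-up.

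The adjustment described in 4.4.2.2 and 4.5 (Poisson regression on baseline characteristics, propensity scores) is written for safety outcomes. It balances who received BDQ, not how the outcome was ascertained. The limitations in section 5 mention routine data that may be lacking, but do not connect this to outcome classification.

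**Working it through.** The protocol gives no figure on this point, so there is nothing to reproduce. The check is an illustration.

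**Inputs**
- S, true treatment success: 48% in both groups, that is, no drug effect (WHO figure in Protocol 1.1.5).
- n: 750 per group (Protocol 4.5, the overlap required for a safety comparison).
- c, the probability that a successful patient has three consecutive negative cultures on record: **assumed**, 80% in the BDQ group and 80%, 75%, 70% or 60% in the non-BDQ group. The protocol gives no culture frequencies.

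**Formulas**
- P(*cured*) = S × c; P(*treatment completed*) = S × (1 − c); the sum is S whatever c is.
- Chance of a false *cured* difference: power of a two-sided 5% test of two proportions.

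**Worked case, 80% v 70%**
- *Cured*: 0.48 × 0.80 = 38.4% v 0.48 × 0.70 = 33.6%; ratio 1.14.
- *Treatment completed*: 0.48 × 0.20 = 9.6% v 0.48 × 0.30 = 14.4%; ratio 0.67.
- Standard error under no difference: √(2 × 0.36 × 0.64 / 750) = 0.0248. The 4.8-point difference is 1.94 standard errors, just below 1.96, so the test rejects about half the time (49%).

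| c, BDQ v non-BDQ | *Cured* | Ratio | *Treatment completed* | Ratio | Chance of false *cured* difference | Success |
|---|---|---|---|---|---|---|
| 80% v 80% | 38.4% v 38.4% | 1.00 | 9.6% v 9.6% | 1.00 | 5% | 48% v 48% |
| 80% v 75% | 38.4% v 36.0% | 1.07 | 9.6% v 12.0% | 0.80 | 16% | 48% v 48% |
| 80% v 70% | 38.4% v 33.6% | 1.14 | 9.6% v 14.4% | 0.67 | 49% | 48% v 48% |
| 80% v 60% | 38.4% v 28.8% | 1.33 | 9.6% v 19.2% | 0.50 | 98% | 48% v 48% |

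The 80% v 70% case gives 61% at 1000 per group and 97% at 3000. If the non-BDQ group were the better documented, the signs would reverse.

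**How culturing frequency maps to c.** Assume 12 post-intensive months, all cultures negative and independent monthly recording. The chance of at least three on record is 44% at a 20% monthly probability and 92% at 40%.

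**Can response move the split too?** Yes. With four cultures on record and a 0%, 10% or 20% chance that each is an isolated positive, the chance of three consecutive negatives is 100%, 80% or 61%. For 10%: 0.9⁴ + 2 × 0.1 × 0.9³ = 0.802.

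**Failure.** Two culture-dependent routes pull in opposite directions as culturing becomes sparser.
- Reversion needs "two consecutive cultures, taken at least 30 days apart, are found to be positive". Assume onset uniform over months 8 to 19, persisting to month 20, with the onset month counted. The chance of two recorded positives falls from 83% at a monthly probability of 0.5 to 54% at 0.25. Fewer failures are seen.
- Conversion needs two recorded negatives. For a patient truly negative over the last five intensive-phase months, the chance falls from 81% at 0.5 to 37% at 0.25. More patients appear not to have converted.

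**The case against.** The strongest reply has four parts.

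- *The robust contrasts are already there.* Treatment success and death sit in the same objective, and 4.4.2.1 describes proportions with intervals, not a test. This stands in part. The 16% and 49% figures describe what a conventional test would do, not a test the protocol states. But the objective is to compare, and nothing ranks success above its two components.
- *Unequal culturing is assumed.* This stands. Patients who decline BDQ share clinics and laboratories with those who take it, and in a stepped wedge a centre may contribute patients before and after access. Section 4.2.2 collects the site of treatment, so stratifying by site can address between-site differences wherever both groups occur within a site.
- *These are WHO definitions.* True, and they are not challenged as reporting categories. The issue is their separate use as between-group contrasts.
- *Culture tables belong in the separate analysis plan.* They may well sit there. The definitions, the absence of a schedule and the list of compared outcomes are fixed in the protocol.

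A reader might infer that these comparisons measure culturing instead of drug effect, or that every category is affected. The protocol supports neither. Each of the two proportions is true success multiplied by documentation, and isolated positives also move the split, so the contrast is a mixture. Death, loss to follow-up and non-evaluation do not depend on the three-culture record.

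**Conclusion.** The point holds in this form: the separate between-group comparisons of *cured* and *treatment completed* for MDR-TB cases mix drug effect with culturing and recording intensity, and the protocol does not separate them. Bias requires culturing to differ between groups. That is not shown. It is plausible for centres without access and less so for decliners at the same sites.

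The size depends entirely on the assumed documentation gap. With 48% success in both groups and 750 per group, a 5-point gap carries a 16% chance of a false *cured* difference and a 10-point gap 49%.

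Treatment success is immune to the split, but not to culture-dependent ascertainment of failure. A reader might infer that sparse culturing lowers failure and inflates success. The definitions do not establish that direction: missed reversions and apparent non-conversions work against each other, and failure also requires that treatment be terminated or at least two drugs be permanently changed, so culture results alone do not assign it.

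**What to change.** In 1.3.1 and 4.4.2.1:

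- Name treatment success and death as the lead between-group effectiveness contrasts.
- Report *cured* and *treatment completed* by group as descriptive results, with no comparative claim.
- Tabulate the number and spacing of post-intensive-phase cultures per patient by group.
- Add one sensitivity analysis, either stratified by site or with cultures thinned to a common interval in both groups.

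An analysis restricted to patients with at least three post-intensive-phase cultures should not be used. It conditions on a post-baseline event, drops patients who died, stopped or failed early, and nearly empties *treatment completed*.

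The cost is wording, one table and one sensitivity analysis, using culture dates already needed to assign the outcomes. Patient care does not change. The downside is that the separate *cured* comparison loses its standing as a primary contrast.

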1.1.4. Main Treatment Options

The WHO-recommended treatment strategy for DS-TB is directly observed treatment short-course (DOTS). DOTS combines 5 elements: political commitment; microscopy services; drug supplies; surveillance and monitoring systems; and use of highly efficacious regimens with direct observation of treatment. The standard WHO chemotherapy treatment regimen for DS-TB consists of a 2-month intensive phase during which 4 drugs are administered once or twice per week (isoniazid, rifampicin, pyrazinamide, and ethambutol), with a continuation phase of 4 months during which 2 drugs are administered (usually isoniazid and rifampicin) to which the mycobacterium has been demonstrated to be sensitive for 4 months (Chan 2002⁶, Douglas 1999⁸). Streptomycin is also used as a first line drug to treat DS-TB, usually for retreatment of newly diagnosed cases that failed to complete the initial treatment course or are responding poorly to their first course of TB treatment.

MDR-TB is considered curable but cannot be adequately treated with the standard short-course therapy (SSCT) (Chan 2002⁶, Douglas 1999⁸). MDR-TB therapy often requires extensive chemotherapy (up to 2 years of treatment) with a combination of less efficacious second line drugs, requires extensive supervision and treatment costs are extremely expensive. Most authorities recommend a regimen consisting of either 3 or 4 oral anti-TB drugs in combination with 1 injectable drug (Frieden 1999¹²).

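### Patients on a long MDR-type regimen whose MDR status is undocumented are scored by the non-MDR outcome rules, which classify the same course differently from the MDR-TB rules

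*Protocol*

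**What the plan says.** Protocol section 4.2.2 gives one set of outcome definitions for MDR-TB cases and then a second: "The following definitions will be used for treatment outcomes among non MDR cases or MDR status not documented". MDR status, or the lack of a record of it, is the only thing that decides which set applies.

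In the second set, Treatment Failed is "A TB patient whose sputum smear or culture is positive at month 5 or later during treatment". Cured needs confirmed TB at the start, plus a negative smear or culture in the final month and on one earlier occasion. Treatment Completed in that set excludes evidence of failure; Cured does not.

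In the MDR-TB set, Treatment Failed begins "Treatment terminated or need for permanent regimen change of at least two anti-TB drugs because of" and lists four reasons: failure to convert within the intensive phase, reversion, acquired resistance to named drug classes, and adverse drug reactions. The time limit for conversion is the programme's own maximum intensive phase. Only failing that does the fallback apply: "If no maximum duration is defined, an 8-month cut-off is proposed". Reversion means that, after conversion, "two consecutive cultures, taken at least 30 days apart, are found to be positive", and it counts only in the continuation phase. Cured needs at least three consecutive negative cultures after the intensive phase and no evidence of failure.

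Section 2.1 defines MDR-TB by in vitro resistance and also states that "all patients initiating BDQ treatment will be eligible for inclusion in the registry regardless of the indication for use". Section 4.2.1 records start dates, stop dates and switches for each drug.

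**The concern.** The second set's failure rule suits a six-month course. Section 1.1.4 describes drug-susceptible treatment as 2 + 4 months and MDR-TB treatment as lasting up to 2 years. A patient started on a long regimen for presumed MDR-TB, with no susceptibility result on file, is nevertheless scored by the short-course rules.

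Such patients can enter. MDR-TB status requires a laboratory result, BDQ starters are admitted whatever the indication, and section 4.2.2 lists documentation of laboratory confirmation as something to be assessed, so gaps are foreseen.

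Two things are at stake. One primary objective in section 1.3.1 is to describe outcomes in the non-MDR/undocumented group. Another is to compare outcomes between BDQ-treated and untreated patients, and it is not limited to MDR-TB. Comparators enter on an MDR-TB diagnosis and BDQ patients on any indication, so patients scored by the wrong set probably lie mainly on the BDQ side.

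**Working it through.** The protocol gives no figure on this point to reproduce. The check applies both sets to the same monthly culture histories.

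**Inputs.** The definitions come from section 4.2.2. Assumed: a completed 20-month regimen (within the 2 years of section 1.1.4), monthly cultures, confirmed TB at the start, and an intensive phase ending at month 4, 5, 6 or 8.

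| History | Second set | MDR-TB set |
|---|---|---|
| Negative from month 3 except one positive at month 5; no drug change | Meets Treatment Failed; also meets Cured | Cured at all four cut-offs |
| Negative from month 3 except one positive at month 12; no drug change | Meets Treatment Failed; also meets Cured | Cured at all four cut-offs |
| Positive through month 5, negative from month 6; no drug change | Meets Treatment Failed; also meets Cured | Cured if the cut-off is 6 or 8 months. At 4 or 5 months the non-conversion criterion is met, but Treatment Failed still needs termination or a two-drug change |
| Negative from month 3; at least two drugs permanently changed for adverse reactions | Cured | Treatment Failed |

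The first three rows show the second set counting failures that the MDR-TB set would not, or would count only on a further condition. The fourth row goes the other way.

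A fifth case needs no coding. A patient who completes a long regimen with only two negative smears, one of them in the last month, is Cured in the second set. In the MDR-TB set, without three consecutive negative cultures, the same patient is Treatment Completed. This shifts patients between categories but leaves Treatment Success, their sum, unchanged.

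**Why regimen length matters.** Suppose each monthly result from month 5 has an independent chance p of being positive. The chance of at least one positive among k results is 1 − (1 − p)^k. Months 5 to 20 give k = 16; months 5 and 6 of a six-month course give k = 2.

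| p (assumed) | k = 16 | k = 2 |
|---|---|---|
| 0.5% | 7.7% | 1.0% |
| 1% | 14.9% | 2.0% |
| 2% | 27.6% | 4.0% |
| 5% | 56.0% | 9.8% |

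For example, at p = 1%: 1 − 0.99^16 = 14.9% and 1 − 0.99^2 = 2.0%. Across this range the single-positive rule is met roughly six to eight times as often on the long regimen. The values of p are illustrative. The table shows how exposure to the rule grows with duration; it does not estimate misclassification in this registry.

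**The case against.** The strongest reply is that the harm is contained. The objective in section 1.3.1 names the same two strata as section 4.2.2, so the plan delivers the description it promises. Section 4.4.2.1 plans the BDQ and non-BDQ outcome proportions for patients with MDR-TB, all scored by one set. It also summarises use outside the MDR-TB indication separately, and no stated analysis pools the two sets. All of this stands. A reader might infer that the objective cannot be answered, or that the main comparison is biased, and the protocol supports neither. What remains is that the second stratum is hard to interpret for its undocumented patients. Section 4.4.2.1 also promises proportions by BDQ status for each objective, and the comparative objective itself carries no restriction to MDR-TB.

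A reader might also infer that the MDR-TB set always allows 8 months to convert. It does not: 8 months is the fallback, and a shorter programme limit makes the late-conversion example conditional, as the third row of the first table shows.

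Finally, it is tempting to quantify inflation of failure. If 5 to 15 in 100 such patients were late converters and true failure were 10%, reported failure would be 15% to 25%, or 1.5 to 2.5 times too high. The protocol gives neither rate, and the sum ignores the errors in the opposite direction, so the inference is unsupported.

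The protocol attributes both sets to a WHO source and says that definitions are still being outlined with WHO (section 4.2). Whether that source assigns the sets by regimen cannot be checked here. The allocation rule is nonetheless written into this protocol, so it is not a detail left to the separate analysis plan.

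**Conclusion.** The point holds as a flaw in a stated rule. Undocumented patients on a long MDR-type regimen are scored by definitions built for a different course of treatment, and identical histories change category depending on whether a laboratory result is on file. For an isolated late positive this is so at every intensive-phase length tried. For late conversion it depends on the programme's cut-off. For drug changes due to adverse reactions the error reverses. Separately, Cured and Treatment Failed are not mutually exclusive in the second set, and a long regimen leaves ample room to meet both.

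The net direction and size are unknown, because the protocol does not say how many undocumented patients to expect. The estimates by treatment within MDR-TB are unaffected. The damage is limited to the non-MDR/undocumented stratum and to any BDQ versus non-BDQ outcome comparison that goes beyond MDR-TB. That affected patients lie mainly on the BDQ side is a reasonable inference from the entry rules, not a documented fact. The change is worth making because it is cheap, but the flaw does not undermine the registry's main outcome estimates.

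**What to change.** In sections 4.2.2 and 4.4.2.1:

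- Score patients of undocumented MDR status who start treatment for presumed MDR-TB by the MDR-TB outcome set. Identify them from the recorded indication and initial regimen, and fix the assignment at treatment start whatever switches follow.
- Keep the second set for documented non-MDR TB and for patients treated as drug-susceptible, including BDQ used outside the MDR-TB indication.
- Make Cured and Treatment Failed mutually exclusive in the second set, for instance by giving Cured the no-evidence-of-failure condition that Treatment Completed already has there.
- Report documented non-MDR and undocumented status as separate strata.
- Limit the BDQ versus non-BDQ outcome comparison to patients scored by the same set.

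The cost is wording in the protocol, carried into the analysis plan, and one more reporting stratum. Indication, drug dates and switches are already to be collected, so no new data are needed.
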